10.3.2.1 Patient Reported Outcomes

Received MDASI-BT forms will be checked versus the timing schedule and considered as valid if they fall within ten days of the scheduled assessment window. Compliance rates will be calculated as the number of received valid forms over the number of expected forms. Differences between groups in compliance will be tested by use of Fisher's exact test at every time point.

We will use descriptive statistics to describe how patients rate symptom severity and interference with function at each time point. Error bar graphs for each of the symptoms will be constructed at each time point. The proportion of patients rating their symptoms to be 5 or greater (on a 0-10 scale) will also be reported. We will construct individual patient profiles for each of the selected

symptoms to describe the individual patients' patterns of change over time. We will calculate the mean symptom severity and mean symptom interference at the time of clinical evaluation. Estimates of differences in the mean symptom severity and mean symptom interference between responders and non-responders will be estimated in the intent to treat population. All patients with at least one valid questionnaire will be included in the analyses. Questionnaires completed at study registration will be considered baseline. All questionnaire data received after randomization will be used in the primary analyses.

Differences of at least 2 points will be classified as the minimum clinically meaningful change in the symptom severity and symptom interference measures. For example, an increase of 2 points or more would mean a moderate improvement, whereas a decrease of 2 points or more would be interpreted as moderate worsening. For individual symptoms, a rise in a symptom score means deterioration, whereas a reduced score means improvement of the specific symptom.

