3.4 QUESTIONNAIRES

MDASI-BT will be completed within 14 days prior to initiating treatment (baseline) and at the time of each imaging study but prior to the patient being informed of the imaging results.

Patients will be asked to continue complete MDASI-BT after treatment discontinuation every 6 months until they are off the clinical trial. This instrument will be available electronically, so patients do not need to come to NIH to complete it after treatment discontinuation.

The MDASI-BT will be completed only by the patient, unless changes in vision or weakness make this difficult. If this occurs, then the caregiver or research assistant may read the questions to the patient or assist with marking the severity number or score as described by the patient. A patient caregiver may complete the questionnaires as a patient-preference proxy if the patient's deficits preclude self-report however, this must be done at every assessment from baseline to end of treatment.

The average time to complete this instrument is 5 minutes. Only for English speaking patients.

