10.3.2 Analysis of the Secondary Endpoint(s)

The similar analyses will be performed for PFS at 12 months as those for PFS6. We will assess the relationship between the neoantigen burden in tumor prior to the treatment and the PFS using the proportional hazard model. The neoantigen burden and HMP status (HMP/NHMP) will be included in the model as the covariates, and their potential interaction will be assessed. Other important baseline prognostic factors will also be included in the model to adjust for the potential confounders. We will evaluate the relationship between the neoantigen burden in tumor prior to the treatment and the objective response using logistic regression with the neoantigen burden and HMP status as covariates. Linear mixed model will be used to examine the trajectory of the longitudinal measures of symptom burden quantified using the MDASI-Brain tumor module. Random intercept will be included to account for the within-subject correlation and HMP status will be included as a covariate.

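### The responder versus non-responder comparison of MDASI-BT scores names no adjustment for the baseline score already collected, so pre-treatment symptom gaps carry into the estimate

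*Combined protocol and SAP*

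**What the plan says.** Section 3.4 schedules the questionnaire: "MDASI-BT will be completed within 14 days prior to initiating treatment (baseline) and at the time of each imaging study". Section 2.4 and footnote 9 of the Section 3.5 calendar agree that a pre-treatment form is collected. Section 3.4 limits the instrument to English speakers.

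Section 10.3.2.1 calculates mean severity and mean interference at clinical evaluations and then states the comparison at issue: "Estimates of differences in the mean symptom severity and mean symptom interference between responders and non-responders will be estimated in the intent to treat population". The same paragraph identifies a baseline form ("Questionnaires completed at study registration will be considered baseline") but does not say that it enters this comparison.

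Section 10.3.2 has a separate longitudinal analysis: "Linear mixed model will be used to examine the trajectory of the longitudinal measures of symptom burden quantified using the MDASI-Brain tumor module". Its terms are given as follows: "Random intercept will be included to account for the within-subject correlation and HMP status will be included as a covariate". Adjustment for baseline factors appears once in Section 10.3.2, in the proportional hazards model for PFS: "Other important baseline prognostic factors will also be included in the model to adjust for the potential confounders".

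**The concern.** Response is an observed outcome, so nothing balances symptoms at entry between those who respond and those who do not. The documents give reasons to expect variation at entry. Eligibility runs from KPS 60 upwards (Section 2.1.1). The two cohorts are assigned different expected disease courses (Section 10.1.1). The first 15 NHMP patients spanned grades 2 to 4 (Section 1.2.7).

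If responders start with fewer symptoms, a difference in follow-up means will contain part of that head start even where response has no association with later symptoms. The baseline score is the obvious covariate for removing this, and the trial already collects it. At stake is how a secondary patient-reported comparison is read, and to a lesser degree its precision.

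**Working it through.** **The plan's own figure.** There is none to reproduce. The documents give no SD, correlation, sample size or power for this comparison.

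**Inputs from the documents**
- At most 59 treated patients (Section 10.1.1.1).
- Scores on a 0 to 10 scale (Section 1.2.5).
- An 8% response rate on nivolumab in the cited recurrent glioblastoma trial (Section 1.2.4). 59 × 0.08 = 4.7, or about 5 responders and 54 non-responders.

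**Assumptions**
- SD of 2 points, equal at baseline and follow-up.
- Baseline-to-follow-up correlation ρ of 0.3, 0.5 or 0.7.
- Responder shares q of 20% and 30% as alternatives to 8%.

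**Step 1: is a baseline gap of about 1 point plausible?** With 5 versus 54 patients, the chance SD of the difference in baseline means is 2 × √(1/5 + 1/54) = 0.93 point. A gap of that size needs no systematic cause.

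**Step 2: carry-over.** With equal variances and no association between response and follow-up score given baseline, the expected unadjusted difference is ρ × D, where D is the baseline gap.

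| D (points) | ρ = 0.3 | ρ = 0.5 | ρ = 0.7 |
|---|---|---|---|
| 0.5 | 0.15 | 0.25 | 0.35 |
| 1 | 0.30 | 0.50 | 0.70 |
| 2 | 0.60 | 1.00 | 1.40 |

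**Step 3: precision.** The ratio of adjusted to unadjusted variance is (1 − ρ²) × [1 + q(1 − q)d²], where d is the baseline gap in SD units.
- Balanced baselines (d = 0): 0.91, 0.75 and 0.51 at ρ = 0.3, 0.5 and 0.7.
- With 5 versus 54, the unadjusted SE of 0.93 becomes 0.89, 0.81 and 0.67.
- With 12 versus 47 (q about 20%), the unadjusted SE of 0.65 becomes 0.62, 0.56 and 0.46.
- With ρ = 0.3 and d = 1 (2 points at SD 2), the ratio at q = 20% is 0.91 × 1.16 = 1.06, and at q = 30% it is 0.91 × 1.21 = 1.10. Here adjustment costs some precision while still removing a carry-over of 0.3 × 2 = 0.6 point.

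**Step 4: simulation check.** 4,000 runs used 59 patients, SD 2, responders 1 point lower at baseline and no association with response. With 12 versus 47 and ρ = 0.5, the unadjusted difference averaged −0.49 (SD 0.65) and the baseline-adjusted difference 0.00 (SD 0.58). Both agree with the formulas.

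**Step 5: does another analysis supply the adjustment?** No. The mixed model describes trajectory by HMP status; its random intercept handles within-patient correlation but gives no baseline-adjusted contrast by response. The covariate adjustment in Section 10.3.2 is for PFS. The individual patient profiles in Section 10.3.2.1 describe change patient by patient and do not compare groups.

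**The case against.** The strongest reply is that this is a descriptive secondary summary with the estimator left open. The plan promises estimates of differences and never calls them unadjusted, so silence should not be read as a deliberate choice of raw means. That is fair as to intent. But a difference in means with no model or covariate named will most naturally be computed from raw means, and nothing else in the plan prevents that.

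Several stronger readings are tempting, and the documents do not support them:

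- **That the plan presents the difference as an effect of response.** It does not use that language; the risk lies in how the result is read.
- **That the difference will be judged against 2 points.** The text says "Differences of at least 2 points will be classified as the minimum clinically meaningful change" and illustrates it with increases and decreases. It does not tie this limit to the responder contrast.
- **That power is lost.** The plan contains no test or power target for this contrast, so a power table would describe an analysis nobody has planned.
- **That adjustment always narrows the interval.** Step 3 of the working shows it can widen by a small amount.
- **That adjustment makes the contrast causal.** Response is classified after baseline and partly on clinical status. Section 6.3.2 and Appendix D require stable or improved clinical status for CR and PR, and count clinical deterioration as progression. Adjusting for baseline removes baseline carry-over and nothing more.

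It is also true that fewer than 59 patients will have scores at any one evaluation. The instrument is English-only, response evaluability requires measurable disease and re-evaluation (Section 10.2.2), and forms become six-monthly after treatment stops. This makes the standard errors above optimistic but does not alter the carry-over formula.

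**Conclusion.** The point holds as a gap in the specification of a secondary comparison. As written, pre-treatment symptom differences between non-randomised groups carry into the responder versus non-responder estimate, by about 0.3 to 0.7 point per 1-point baseline gap for ρ between 0.3 and 0.7. That range rests on assumed correlations and equal variances. The actual gap, its direction, the SD and the responder share in this trial cannot be taken from the documents.

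The gain in precision is likely but secondary: 9%, 25% or 49% less variance at ρ = 0.3, 0.5 or 0.7 with balanced baselines, against 6% to 10% more in the unfavourable case of ρ = 0.3, a 1-SD imbalance and 20% to 30% responders. The PFS6 decision rules are not affected.

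**What to change.** In Section 10.3.2.1, state that at each evaluation mean severity, and separately mean interference, will be regressed on responder status, the patient's baseline value of the same score and HMP status. Report the adjusted difference with its 95% CI and label it a descriptive association, not an effect of response. Keep the raw means by group, so that patients with a valid form but no baseline form are still reported; Section 10.3.2.1 includes anyone with at least one valid form.

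The same edit should settle which form is the baseline. Sections 2.4, 3.4 and 3.5 use the 14 days before treatment, while Section 10.3.2.1 refers to study registration.

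The cost is a few sentences and no new data or visits. Each covariate uses one degree of freedom, which matters somewhat with few responders, and patients without a baseline form drop out of the adjusted estimate.

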1.1.2 Secondary Objectives

- To determine the 1-year progression free survival rate and overall survival in IDH-mutant gliomas patients with and without HMP in response to nivolumab treatment.
- To determine whether the neoantigen burden in tumor prior to the treatment is correlated with treatment response.
- To longitudinally evaluate patient reported outcome measures using self-reported symptom severity and interference with daily activities using the MDASI-BT.

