1.2.5 Rationale for the patient-reported outcome studies

Precedence for measuring “non-therapeutic” endpoints exists in oncology research. For example, Gemcitabine was approved by the FDA partially as a consequence of the decrease in pain reported in pancreatic patients who were treated, not on the basis of survival improvement, which was

modest, at best. There have been efforts in neuro-oncology to evaluate secondary endpoints using validated instruments as an additional indicator of benefit.

The M.D. Anderson Symptom Inventory-Brain Tumor Module allows the self-reporting of symptom severity and interference with daily activities. The MDASI-BT has demonstrated reliability and validity in the adult primary brain and spine tumor patient population. [42, 43] This tool represents a modification of the widely used and validated M.D. Anderson Symptom Inventory, with particular attention to symptoms common in patients with brain and spine tumors respectively.

The MDASI consists of symptoms rated on an 11-point scale (0 to 10) to indicate the presence and severity of the symptom, with 0 being “not present” and 10 being “as bad as you can imagine.” Each symptom is rated at its worst in the last 24 hours. Symptoms included on the instrument include those commonly associated with cancer therapies, those associated with increased intracranial pressure, and those related to focal deficits. The questionnaire also includes ratings of how much symptoms interfered with different aspects of a patient’s life in the last 24 hours. These interference items include general activity, mood, work (includes both works outside the home and housework), relations with other people, walking, and enjoyment of life. The interference items are also measured on 0 - 10 scales. The average time to complete these instruments is 5 minutes. The MDASI-BT has been translated into multiple languages, but the English language version will be used for this study. In addition, information regarding demographics and treatment history will be collected as part of the larger study and used in this analysis.

The availability of validated instruments provides an opportunity to prospectively assess the impact of treatment, both positive and negative, on patients. The evaluation of symptom burden in this study will assist in finding the best possible treatment with the least toxicity.

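### The 2-point MDASI-BT rule runs backwards: it labels a rise in symptom severity or interference as improvement and a fall as worsening

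*Combined protocol and SAP*

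**What the plan says.** Section 1.1.2 lists a secondary objective: "To longitudinally evaluate patient reported outcome measures using self-reported symptom severity and interference with daily activities", with the MDASI-BT as the instrument. Section 1.2.5 describes how it is scored. Symptoms are "rated on an 11-point scale (0 to 10) to indicate the presence and severity of the symptom", where 0 means the symptom is absent and 10 means it could not be worse. A second set of items asks to what extent symptoms interfered with six areas of life, and "The interference items are also measured on 0 - 10 scales".

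Section 10.3.2 gives the model: "Linear mixed model will be used to examine the trajectory of the longitudinal measures of symptom burden". Section 10.3.2.1 adds descriptive analyses, including mean severity and mean interference, and fixes 2 points as the smallest clinically meaningful change on both measures. It illustrates the threshold by saying that "an increase of 2 points or more would mean a moderate improvement". For a change in the other direction, its reading is that "a decrease of 2 points or more would be interpreted as moderate worsening". The sentence after that says: "For individual symptoms, a rise in a symptom score means deterioration", and that a lower score is an improvement of that symptom.

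**The concern.** The labels in the 2-point rule run against the scale. On an instrument where larger numbers mean worse symptoms, a rise cannot be an improvement. The paragraph also contradicts itself, because its next sentence gives the opposite direction for individual symptoms.

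That later sentence is limited to individual symptoms. For interference, the reversed wording is the only statement of direction in the analysis section.

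What is at stake is interpretation. Severity and interference over time are a stated secondary objective, and section 1.2.5 wants the instrument to show both benefit and harm of treatment. A reader or programmer who applied the rule as written would report a change of 2 or more points in the wrong direction.

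**Working it through.** There is no plan figure to reproduce. The check compares the direction of the scale with the direction in the rule.

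**Inputs**
- Severity items: 0 to 10, 0 = absent, 10 = worst imaginable (1.2.5).
- Interference items: 0 to 10, rating the extent of interference (1.2.5). Six are listed: general activity, mood, work, relations with others, walking, enjoyment of life.
- Threshold: 2 points on severity and on interference (10.3.2.1).
- Reverse coding, or any MDASI-BT score on which higher is better: none described.

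**Step 1: direction.** Let d = later score minus earlier score.

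| Source | d of +2 or more | d of −2 or less |
|---|---|---|
| Severity anchors, 1.2.5 | worse | better |
| Interference description, 1.2.5 | worse (inferred) | better (inferred) |
| 2-point rule, 10.3.2.1 | improvement | worsening |
| Individual-symptom sentence, 10.3.2.1 | deterioration | improvement |

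The 2-point rule is the only row that points the other way. The interference row is marked as inferred because 1.2.5 gives verbal anchors for the symptom items only. A rating of how far symptoms interfered has no other natural reading.

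**Step 2: the paragraph cannot be satisfied for severity.** Mean severity over k items changes by d_mean = (d_1 + … + d_k) / k. If every item rises by 2, then d_mean = 2k / k = 2. Each item is then a deterioration by one sentence, and their mean is an improvement by the other. A mean keeps the direction of its items, so both cannot hold.

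**Step 3: an interference example (scores assumed for illustration).** Let mean interference go from 2 to 4.
- Item total before: 6 × 2 = 12. After: 6 × 4 = 24, out of 6 × 10 = 60.
- Net rise: 24 − 12 = 12. One item can rise by at most 10, and 12 / 10 = 1.2, so at least 2 items must have risen.
- An attainable case is (0, 0, 3, 3, 3, 3) going to (6, 6, 3, 3, 3, 3). Two items are worse, four are unchanged and none is better.
- Label under the written rule: moderate improvement.

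**Step 4: reach.** Sections 10.3.2 and 10.3.2.1 name seven outputs based on the scores: the mixed-model trajectory, descriptive statistics, error-bar graphs, the proportion scoring 5 or more, individual profiles, mean severity and interference, and responder versus non-responder differences. They also name two on compliance: the rates and Fisher's exact test. None of these 7 + 2 = 9 uses the improvement or worsening label in its calculation, so 0 of 9 change numerically.

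**The case against.** The best case on the other side accepts that the two words are transposed and argues that it hardly matters.

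- **The operative sentence is sound.** The 2-point threshold is stated without a direction, and the reversed wording is offered as an example. This is true, but the example is the only place where the plan says what a 2-point change on these measures means.
- **The slip is easy to spot.** The next sentence gives the right direction for individual symptoms, the scale is defined in the same document, and the planned report of scores of 5 or more treats high scores as bad. This makes misuse for severity unlikely. It is weaker for interference, where an analyst must go back to section 1.2.5 and infer the direction. In either case a prespecified rule should not depend on someone overriding it, and a departure made after the data are seen would need explaining.
- **Nothing numerical depends on it.** No patient-reported success criterion, model, sample size or stopping boundary uses the label. This stands in full and limits the weight of the point.
- **The interference example adds no evidence of numerical impact.** That is fair. Any change of +2 shows the same sign error, and the example only illustrates it.

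**Conclusion.** The concern holds. As written, the meaningful-change rule in 10.3.2.1 is reversed for both measures it covers. It conflicts with the scoring in 1.2.5 and with the sentence that follows it.

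The size is limited to the verbal label on a change of 2 or more points in a secondary outcome. No patient-reported result changes in value, no tabulation of improved and worsened patients is planned, and PFS6 and the two-stage designs are unaffected.

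The conclusion rests on two readings: that scores are analysed as collected, since no reverse coding is described, and that a higher interference rating means more interference. It is a wording error that should be fixed, because the text is the current interpretation rule for a stated secondary objective and the correction is nearly free.

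**What to change.** In 10.3.2.1, exchange the two labels so that the sentence reads, in substance: *on both the severity and the interference measures, a rise of at least 2 points is a moderate worsening and a fall of at least 2 points is a moderate improvement*. Keep the 2-point threshold and its scope as they are. The sentence on individual symptoms can stay, since the two will then agree. Naming interference explicitly also supplies the direction that the analysis section now lacks.

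The cost is two words in one sentence. Data collection, sample size, the planned models and the budget are unaffected. The change is best made before any patient-reported results are interpreted.

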10.3.3 Safety Analyses

The type and grade of AE will be summarized using frequency tables.

10.3.4 Planned Interim Analyses

For the HMP cohort, the trial is carried out in two stages. In stage I, a total number of 10 patients is accrued. If 9 or more patients progressed by 6 months, the cohort will be terminated early; otherwise, additional 19 patients will be accrued in stage II, resulting in a total sample size of 29. Among these 29 patients, if 6 or more patients are progression free at 6 months, we reject the null hypothesis and claim that the treatment is promising for patients with HMP IDH-mutant gliomas.

For the NHMP cohort, the trial is carried out in two stages. In stage I, a total number of 15 patients is accrued. If 3 or more patients are progression-free at 6 months, the cohort will be moved to stage II and additional 15 patients will be accrued in stage II, resulting in a total sample size of 30. Among these 30 patients, if 10 or more patients are progression free at 6 months, we reject the null hypothesis and claim that the treatment is promising for patients with NHMP IDH-mutant gliomas.

